## Inclusion criteria are:

- (1) Singleton living full-term fetus.
- (2) Cephalic presentation,
- (3) Bishop score less than 5,
- (4) Assuring fetal monitoring,
- (5) The mother does not have PROM,

#### The exclusion criteria are;

- (1) Expected fetal anomaly (eg. by ultrasound),
- (2) Abnormal presentation,
- (3) Multiple pregnancy,
- (4) Non assuring fetal CTG,
- (5) Fetus more than 90th percentile of expected weight,
- (6) Previous maternal obstructed labor or previous cesarean section,
- (7) Maternal obstetric or medical complication,
- (8) Structural anomaly of the uterus

Any woman with other general or obstetric risk will be excluded. The women that fulfill these criteria will be admitted to the hospital for induction of labor.

## Assessment:

The women who fulfill the inclusion criteria will undergo a thorough assessment and evaluation as follow:

1- History: personal, medical and detailed obstetric history. Previous history of obstetric or medical complication with pregnancy and expectance of recurrence should be considered.

- 2- General examination: for vital signs and cardiopulmonary diseases.

  General signs of other complications (eg. anemia with pregnancy) should be taken in consideration.
- 3- Obstetric examination: fundal level and pelvic grip for assessment of fetal size and lie. Vaginal exam will be done to assess the presentation and scoring the cervix according to Bishop's score:

(Table):Bishop score for cervical assessment(Williams Obstetrics, 23rd ed)

Score	Cervical Dilation	Cervical Effacement	Station of Baby	Cervical Posi- tion	Cervical Consistency
0	closed	0-30%	-3	posterior	firm
1	1-2cm	40-50%	-2	mid-line	moderately firm
2	3-4cm	60-70%	-1,0	anterior	soft (ripe)
3	5+ cm	80+%	+1, +2		

Add 1 point to overall score for pre-eclampsia and for each prior vaginal delivery.

Subtract 1 point off overall score do postdate pregnancy, no prior births, premature or prolonged rupture of membranes (water breaking).

A score of 5 or less is said to be "unfavorable." Unfavorable scoring shows mother is a candidate for cervical ripening prior to induction. A score of 6 or higher would indicate that the cervix is ripe and induction would have a higher probability of being successful. A score of 9 or higher indicates a very high probability of induction being successful.

#### Method:

After approval of Ethics Committee of Scientific Research, the women under the study will be informed about the study plan and possible

benefits and adverse effects. After having an informed consent, they will be *randomized* into two groups receive either nitroglycerine skin patch (Nitroderm TTS® 5mg, Novartis) or a placebo patch.

Group A: will receive nitroglycerine skin patch at time of admission plus induction with dinoprostone 3mg (Dinoglandin® 3gm, Rotabiogen) / 8 hours vaginal tablet into the posterior fornix of the vagina.

Group B: will receive placebo patch at time of admission plus induction with dinoprostone 3mg (Dinoglandin® 3gm, Rotabiogen)/8 hours into the posterior vaginal fornix.

#### Allocation and Concealment:

Both nitroglycerine and placebo patches will be randomized according to a sequence of random numbers generated by computer. They will be enclosed in opaque, sealed, easy opening envelopes. Each envelope contains either a nitroglycerine skin patch or a placebo patch. Opening the envelope at the moment the mother enters the labor ward for induction of labor. The intervention and control groups and the investigator will be blinded about which patch the women will be assigned to.

#### Randomization and Administration:

Both placebo and Nitroderm TTS® patches will be identical in appearance. They are randomly numbered and delivered to the residents in the admission ward. The resident obstetrician is asked to deliver the patch to the mother to apply it on the upper chest.

At the same time, dinoprostone (as Dinoglandin E2® Rotabiogen 3mg vaginal tablet) will be administered into the posterior fornix of the vagina after soaking it with gel. Another dose will be given after 8 hours according to Ain Shams University Hospital protocol for labor induction. Neither the mother nor the obstetrician would know which patch is given.

## Evaluation of the effect:

Assessment of the cervix will be done at the second dose and after 12 and 24 hours through the changes and progression of the Bishop's score. A *blank table of Bishop's score* will be delivered to the examiner who will be asked to fill the table according to the cervical state. The table will be filled twice for every patient. Data will be collected at the end of the study for final assessment of the results.

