# **Aim and Objectives:**

Aim: This study aims to establish the efficacy of nitroglycerine skin patch as a NO donor in addition to dinoprostone for induction of labor.

Objectives: The primary outcome of the study is to compare the changes occurring to the cervix through the progression in the Bishop's score between NO donor (nitroglycerine patch) vs placebo; in combination with a well-established method of induction (Dinoprostone).

The secondary objective of the study is to observe and report possible fetal and maternal side effects that may be associated. This will establish the safety and tolerability of NO donors.

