#### **Management and Monitoring:**

If the case managed to initiate labor, reevaluation of the mother and the fetus will be carried out. And the mother will be monitored according to routine management via the partogram.

If there is a progression in the Bishop's with no onset of labor, induction will be initiated by amniotomy. Provided that the liquor is clear, oxytocin intravenous drip will be initiated. If the liquor is meconium stained, thorough fetal monitoring will take place. Persistent abnormal fetal CTG or deeply stained liquor will be referred to theater for cesarean section.

The fetus will be monitored by the cardiotocography. The mother will be evaluated by the vital signs and other signs of headache, palpitation, dizziness, GI upset ....etc.

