#### **Data presentation and Statistical Methods:**

Data will be collected, tabulated, then analyzed using PC using Statistical package for Social Science (SPSS 15.0.1 for windows; SPSS Inc, Chicago, IL, 2001).

Normally distributed numerical data will be presented as mean and SD, and skewed data as median and interquartile range. Qualitative data will be presented as number and percentage.

Comparison between the means will be done by paired t test for independent samples. Skewed data will be compared using the Mann-Whitney test. Categorical data will be compared using the chi-squared test for qualitative data comparison.

A p-value <0.05 will be considered statistically significant.

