# Both groups will be compared regarding:

- Time from the start of labor induction to vaginal delivery
- > Time from start of drug administration to the earliest uterine contraction
- ➤ Progression of Bishop's score
- ➤ Duration of the first, second and third stages of labor
- ➤ Whether they eventually need to have a cesarean section or not.
- ➤ Incidence of maternal complications, namely; headache, nausea, postpartum hemorrhage,
- > Neonatal outcome through Apgar score at 1 and 5 minutes after delivery.

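### The primary Bishop score does not exist for women who deliver before the 12 or 24 hour assessment, and the protocol names neither a primary time point nor a rule for them

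*Protocol*

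**What the plan says.** All places are in the protocol.

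- Aim and Objectives: the primary outcome is to "compare the changes occurring to the cervix through the progression in the Bishop's score" between patch and placebo. No time point is attached.
- Evaluation of the effect: "Assessment of the cervix will be done at the second dose and after 12 and 24 hours". The same paragraph then says: "The table will be filled twice for every patient". Three assessment times and two completed tables do not agree.
- Randomization and Administration, which places the second dose: "Another dose will be given after 8 hours according to Ain Shams University Hospital protocol for labor induction". The scores therefore fall at about 8, 12 and 24 hours.
- Management and Monitoring: "If the case managed to initiate labor, reevaluation of the mother and the fetus will be carried out", after which "the mother will be monitored according to routine management via the partogram". Progression of the score without labour leads to amniotomy and, if the liquor is clear, oxytocin. Some women go to caesarean section. Nothing is said about Bishop scoring after any of these events.
- Both groups will be compared regarding: the list includes "Time from the start of labor induction to vaginal delivery" and the need for caesarean section.
- Data presentation and Statistical Methods: "Comparison between the means will be done by paired t test for independent samples", with Mann-Whitney for skewed data and chi-squared for categorical data. I read the t test as the two-sample test. No value, rank or category is given to a woman who has delivered.

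**The concern.** Delivery is the purpose of the treatment, so some deliveries before 24 hours are foreseeable. After delivery there is no cervix to score, however complete the follow-up. This is a gap in the definition of the primary endpoint, more than the handling of an occasional missing value.

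Who is lost depends on response. The Assessment section says that a higher score makes successful induction more likely, and Management and Monitoring makes progression itself the trigger for amniotomy. If the patch works, more patch women may leave the comparison early, and those left would be the slower responders. The randomised groups are then no longer what is compared.

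With the time point and the treatment of delivered women both open, either could also be settled after the data are seen, and either could change the primary result.

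**Working it through.** **The plan's own figures.** The only quantitative anchor is in Sample Size Justification: favourable cervix 41% against 81%, two-sided alpha 0.05, power 0.8, 45 per group. The usual two-proportion formula gives 23 per group (27 with continuity correction), so 45 does not follow from these inputs. The present point does not rest on 45. At the planned 50 per arm (100 women), power for 41% against 81% is 0.99.

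**Mean score change.** The documents give no mean gain, SD or early-delivery rate, so these are assumptions: gain 4.5 points (placebo) and 6.0 (patch), SD 2.5, true effect 1.5, 50 per arm. Full-data power of the t test is 0.84.

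Suppose a woman is lost when a normally distributed tendency to deliver, correlated r with her gain within arm, exceeds a cut-off. Let z be the standardised cut-off. Then

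- share lost = 1 − Φ(z)
- mean gain of those kept = μ − r × 2.5 × λ, with λ = φ(z)/Φ(z)
- observed effect = 1.5 − 2.5 r (λ_patch − λ_placebo)

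With r = 1 and a cut-off at a gain of 7.5, z = (7.5 − 4.5)/2.5 = 1.2 for placebo and (7.5 − 6.0)/2.5 = 0.6 for patch. The shares lost are 11% and 27%, and λ is 0.219 and 0.459. The observed effect is 1.5 − 2.5 × 0.240 = 0.90. A cut-off at 6.0 gives 27% and 50% lost, λ 0.459 and 0.798, and an effect of 1.5 − 2.5 × 0.339 = 0.65. Holding the loss rates and weakening r gives the following (power by simulation):

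| Lost, placebo / patch | r | Observed effect | Power |
|---|---|---|---|
| none | – | 1.50 | 0.84 |
| 11% / 27% | 1 | 0.90 | about 0.54 |
| 11% / 27% | 0.6 | 1.14 | about 0.57 |
| 11% / 27% | 0.3 | 1.32 | about 0.68 |
| 27% / 50% | 1 | 0.65 | about 0.30 |
| 27% / 50% | 0.6 | 0.99 | about 0.38 |
| 27% / 50% | 0.3 | 1.25 | about 0.48 |

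Part of the power loss is only the loss of observations. With r = 0 and 11%/27% lost, about 44 and 36 women remain. The effect stays 1.5, and the standardised signal is (1.5/2.5) × √(44 × 36/80) = 2.67, so power is about Φ(2.67 − 1.99) = 0.75. The rest of the fall, to 0.54–0.68, is due to selection.

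**Rank alternative.** With delivered women given the best rank in a Mann-Whitney test and r = 1, power is 0.82 at 11%/27% lost, about 0.78 at 27%/50% and 0.71 at 50%/73%. The type I error is about 5%.

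**Favourable-cervix scale.** Take 41% as placebo and 81% as patch (the protocol does not label them). Let shares e_c and e_t deliver before the assessment, all with a favourable cervix, and be left out. The observed difference is

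(0.81 − e_t)/(1 − e_t) − (0.41 − e_c)/(1 − e_c) = 0.59/(1 − e_c) − 0.19/(1 − e_t).

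| e_c / e_t | Difference (points) |
|---|---|
| 0 / 0 | 40.0 |
| 10% / 10% | 44.4 |
| 10% / 20% | 41.8 |
| 20% / 40% | 42.1 |
| 10% / 30% | 38.4 |
| 10% / 50% | 27.6 |
| 20% / 60% | 26.3 |

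The difference falls below 40 only if e_t exceeds about 26% when e_c is 10%, or about 44% when e_c is 20%. Power is 0.94 at 10%/30%, 0.61 at 10%/50% and 0.52 at 20%/60%.

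**The case against.** A reader might infer that the protocol drops the best responders and that any patch effect must shrink. The documents support neither statement.

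- **Silence is not exclusion.** No section says that delivered women are left out. Omission is only what the named tests do by default when a score is absent, and an SAP that is not shown might hold a rule. The point about silence stands. The appeal to the SAP has less force, because the outcome itself is undefined for a foreseeable, response-dependent group, and the outcome and its timing are what a protocol should fix.
- **Direction is not certain.** On the favourable-cervix scale the difference can hold or grow, as shown above. Women sent to caesarean also lose later scores and need not be good responders. Amniotomy and oxytocin follow progression in both arms, so later scores also reflect co-treatment. This stands.
- **The steepest figures are a worst case.** They assume that the highest gains are always the ones lost. At weaker dependence the bias is smaller and more of the power loss comes from numbers alone. This stands, and the tables show the range.
- **The 8-hour score is probably much less exposed**, since women enter with a score below 5. Because no primary time is named, bias at 12 or 24 hours is not yet bias in the primary comparison. This stands too, and is itself a reason to name the time point.

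**Conclusion.** The point holds as a badly fixed endpoint. The primary outcome has no named time point and is undefined for women who deliver before a scheduled score. The natural default would compare groups selected after randomisation. For the mean score change, bias towards no effect and a loss of power are probable, provided that delivery tracks ripening and the patch speeds delivery. Under the lightest loss assumed (11% against 27%), a true effect of 1.5 points appears as about 0.9 to 1.3, with power about 0.54 to 0.68 instead of 0.84. Heavier loss does more harm. These sizes rest entirely on assumed gain, SD, loss rates and correlation. Neither the actual size nor, on the favourable-cervix scale or with caesareans, the direction can be settled from the documents.

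**What to change.** In Evaluation of the effect and in Data presentation and Statistical Methods:

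1. Name one primary time point. The second-dose score is probably least affected; 12 and 24 hours can then be secondary under the same rules.
2. Reconcile the three assessment times with the table being completed twice.
3. Analyse all randomised women at that time point.
4. Give women delivered vaginally before it the best rank in a Mann-Whitney test, or count them as favourable if the binary comparison is used.
5. Keep the measured score of women who are in labour but undelivered. Their cervix can still be scored, and ranking them as delivered would discard real data.
6. After a caesarean before that time, carry forward the last recorded score, with lowest rank as a sensitivity analysis.

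The cost is a few sentences, with no change to care or sample size. The small downside is that the primary result becomes a rank comparison instead of a mean difference in points. The mean difference among scored women can still be reported as descriptive.

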#### **Management and Monitoring:**

If the case managed to initiate labor, reevaluation of the mother and the fetus will be carried out. And the mother will be monitored according to routine management via the partogram.

If there is a progression in the Bishop's with no onset of labor, induction will be initiated by amniotomy. Provided that the liquor is clear, oxytocin intravenous drip will be initiated. If the liquor is meconium stained, thorough fetal monitoring will take place. Persistent abnormal fetal CTG or deeply stained liquor will be referred to theater for cesarean section.

The fetus will be monitored by the cardiotocography. The mother will be evaluated by the vital signs and other signs of headache, palpitation, dizziness, GI upset ....etc.

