## Sample Size Justification:

The study was calculated using STATA® version 11 program, setting the type-1 error at 0.5 and the power  $(1-\beta)$  at 0.8. Sample size is correlated to former studies in induction of labor (Collingham et al., 2010). Calculation according to these values produced a minimal sample size of 45 cases in each group.

Alpha error= 0.05 (two sides) Power of study= 0.8

Based on favorable outcome of cervix (p1= 41%, p2=81%) with ratio of intervention group to control group 1:1.

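### Three planned Bishop assessments share two filled tables, and augmentation starts on an unquantified rise in the same score, so a written post-baseline, pre-augmentation score is not assured

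*Protocol*

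**What the plan says.** Aim and Objectives makes progression of the Bishop score, nitroglycerine patch against placebo on top of dinoprostone, the primary outcome.

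On when the score is taken, Evaluation of the effect says: "Assessment of the cervix will be done at the second dose and after 12 and 24 hours". Randomization and Administration places the second dose: "Another dose will be given after 8 hours according to Ain Shams University Hospital protocol for labor induction". On what is written down, Evaluation of the effect says: "The table will be filled twice for every patient". An admission score is also taken (Assessment), because entry requires a score below 5.

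On augmentation, Management and Monitoring says: "If there is a progression in the Bishop's with no onset of labor, induction will be initiated by amniotomy". It continues: "Provided that the liquor is clear, oxytocin intravenous drip will be initiated". Neither sentence gives a number of points, a cut-off or a time.

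The only ripeness limit is in the note to the Bishop table under Assessment: "A score of 6 or higher would indicate that the cervix is ripe". The amniotomy rule does not refer to it.

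**The concern.** There are two defects, and each makes the other worse. First, the recording instruction contradicts the assessment schedule, so a site that follows the text loses part of the primary outcome. Second, the score that measures the outcome also triggers a co-intervention that can move it. An arm that ripens faster may receive amniotomy and oxytocin earlier or more often, and its later scores may then include their effect.

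The Research Question asks both whether the patch enhances ripening and whether it facilitates induction. A score taken under augmentation speaks to the second part. Only a score taken after baseline and before augmentation isolates the first. If that score and the augmentation times are not written down, no later analysis can recover them.

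**Working it through.** **1. Examinations against tables.** The inputs are three post-baseline assessments and two tables (Evaluation of the effect), one admission score (Assessment) and 100 women (Methodology).

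- If both tables are for post-baseline examinations: 3 − 2 = 1 planned score per woman unrecorded. Over the trial, 100 × 3 = 300 planned against 100 × 2 = 200 recorded.
- If the admission score uses one table: 4 − 2 = 2 unrecorded per woman, or 400 planned against 200 recorded.

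These totals assume that every woman reaches every examination. Women who deliver before 24 h would have fewer.

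**2. Which readings leave out a post-baseline, pre-augmentation score.** The text does not say which examinations are recorded, or at which one amniotomy is decided. Listing the possible pairs gives:

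| Amniotomy decided at | Two tables from 8, 12, 24 h | Baseline plus one of 8, 12, 24 h |
|---|---|---|
| 8 h | 1 of 3 pairs lacks it (12 and 24 h) | 2 of 3 lack it (12 h; 24 h) |
| 12 h | 0 of 3 | 1 of 3 (24 h) |

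These are counts of readings, not probabilities. Three of the four combinations allow the score to be missing, and the text rules none of them out.

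**3. Can the size be estimated?** The Protocol gives no score distribution, no augmentation rate and no effect of augmentation on the score, so it cannot. A simulation on assumed inputs serves only to show how a threshold behaves.

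- Assumed inputs: baseline uniform on 0–4 or 2–4; 8 h gain with mean 1.5 or 2.5 and SD 2; patch adds 1 point by 8 h and nothing later; 8–12 h gain with mean 1 and SD 1.5, floored at 0; score held within 0–13; augmentation at 8 h for every woman who meets the trigger, adding 1, 2 or 4 points by 12 h; 600,000 women per arm; 12 input sets per trigger.
- Formula: ratio = (12 h difference between arms with augmentation) ÷ (12 h difference without it).

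| Trigger | Ratio, mean score | Ratio, standardized mean difference |
|---|---|---|
| Any rise | 1.07 to 1.55 | 0.98 to 1.13 |
| Score of 6 or more | 1.14 to 1.59 | 1.00 to 1.04 |

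If augmentation adds nothing, every ratio is 1.00. With no patch effect and 50 women per arm, the t test rejects at about 0.05, its nominal level.

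Two things follow whatever the exact inputs: one blinded rule for both arms creates no false signal, and a cut-off of 6 does not remove the effect of augmentation on the mean. The ranges reflect the assumptions and do not estimate this trial.

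**The case against.** **The later scores may still be clean.** The second tablet is scheduled at 8 h, and nothing says that amniotomy replaces it. If amniotomy waits for the 12 h examination, the 12 h score is also pre-augmentation, and any two tables from 8, 12 and 24 h include a usable score. This is a fair reading. The Protocol does not state it, and it still fails if one of the two tables is the baseline.

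**Total-strategy scores are legitimate, and analysis choices belong in an SAP.** This stands for the choice of primary time point and for the handling of augmented women. It does not cover which examinations are written down: the Protocol itself fixes that, in contradiction to its own schedule, and no SAP can restore an unrecorded score.

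**Stronger readings that the document does not support.**

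- *The amniotomy rule conflicts with the ripeness limit.* Assessment says of a score of 5 or less: "Unfavorable scoring shows mother is a candidate for cervical ripening prior to induction". A reader might infer that amniotomy after a one-point rise breaks this. But the note concerns initial assessment, and by the time of amniotomy every woman has had dinoprostone. Progression can also be read as progression to a ripe cervix.
- *A large share of women would be augmented while unripe.* On the assumptions above, the any-rise reading puts 34% to 50% of control women in that position at 8 h. That ignores the condition that labor has not begun. With an assumed 25% in labor by 8 h, independently of score, the range is 26% to 37%; with 50%, it is 17% to 25%. The document supports none of these figures.
- *There are two competing endpoints, distorted differently.* The favorable-cervix proportion appears only as a sample-size input, without a cut-off, and is not listed as an outcome.
- *The trial is biased toward a positive result.* The mother and the obstetrician are blinded, so the rule creates no false signal under the null.

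**Conclusion.** The point holds on the wording. Evaluation of the effect contradicts itself, and following it loses at least one planned primary-outcome score per woman (two if the baseline uses a table), without saying which. Management and Monitoring allows augmentation on an undefined rise in that same score, so later scores may include augmentation, and a written post-baseline, pre-augmentation score is not assured.

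The consequence is limited. Provided the blinding works as described, there is no false signal if the patch does nothing. If the patch works, the design limits how far a 12 h or 24 h difference can be attributed to ripening, by an amount that cannot be estimated from the document. Confidence is high on the wording defects; no size is claimed for the distortion. The change should be made before enrolment, because the missing data cannot be recovered afterwards.

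**What to change.** **Evaluation of the effect.** Replace the two-table sentence with a requirement for a completed Bishop table at baseline, at the second dose (before the tablet is inserted), at 12 h, at 24 h, and immediately before any amniotomy or oxytocin. Record the start times of amniotomy and oxytocin. State what is entered for a woman who is in labor or has delivered before a scheduled examination.

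**Reporting.** Show the 8 h score, or the last score before augmentation, by arm beside the 12 h and 24 h scores. Label the latter as results under the whole induction strategy and give augmentation use by arm. Whether 8 h becomes the primary time point is for the sponsor to decide.

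**Management and Monitoring.** State the amniotomy criterion, for example a score of 6 or more, taken from the Protocol's own ripeness limit and subject to clinical confirmation. This is a useful clarification, but it does not replace the extra tables, because it leaves the effect of augmentation on the mean score in place.

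**Cost.** A few extra recorded fields, mostly at examinations already made, and short wording changes in two sections. Sample size and treatment arms are unchanged.
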